3.4.1.4 Additional Analyses of the Primary Efficacy Endpoint(s)

The following additional analyses will be performed to assess the sensitivity of the assumptions of the statistical methods used in the primary efficacy analysis. Firstly, a supplementary analysis using the ITT population will be done using all available data from subjects irrespective of whether or not they completed treatment, including data collected after subjects received rescue therapy. An MMRM followed by a MCP-Mod dose response model will be used for the analysis and the results from the fitted dose response model and the MMRM will be presented in a similar way as described above for the analysis of the primary efficacy endpoint (Section [3.4.1.3](#)).

A second supplementary analysis will be performed using the ITT population. Data from assessments performed after prohibited or rescue therapies are received will be excluded and a last observation carried forward (LOCF) approach will be applied for the missing data. An ANCOVA followed by a MCP-Mod dose response model including treatment group and

randomization stratum (total serum IgE level < 150 kU/L or ≥ 150 kU/L) as categorical factors and baseline EASI score as covariate, with 4 candidate models for the dose response (linear, E_{\max} , and 2 Hill- E_{\max} models) will be used for the analysis. The results from the fitted dose response model and the ANCOVA will be presented in a similar way as described above for the efficacy analysis for the primary endpoint (Section 3.4.1.3).

A third supplementary analysis will be performed using the ITT population, excluding data from subjects CCI whose treatment allocations were accidentally unblinded at the site. All other details of this analysis are the same as those for the primary analysis (Section 3.4.1.3).

A fourth supplementary analysis for percent change in EASI score will be performed using a MMRM as described above (Section 3.4.1.3), including data from visits up to Week 24. The ITT population will be used for the analysis and data from visits after subjects receive rescue therapy will be excluded from the analysis. From the final model obtained from the fitted MMRM, the adjusted difference in mean percent change from baseline in EASI score between the placebo and each MEDI3506 group at each visit will be estimated along with the 90% CI and two-sided p-value. A plot of the adjusted mean percent change from baseline (\pm SE) in EASI by visit will be provided.

In addition, similar summary (MMRM) will be provided for each of the four components of EASI (ie. erythema, papulation, excoriation and lichenification).

3.4.1.5 Subgroup Analyses

The consistency of the overall treatment effect on the primary endpoint will be assessed in subgroups of subjects. A MMRM, as described in Section 3.4.1.3, including data from up to Week 16, will be used for each subgroup. The analyses will be performed for subgroups, as follows:

- Total serum IgE level at baseline (< 150 kU/L vs ≥ 150 kU/L).
- Baseline IGA score (3 vs 4).
- Baseline EASI (≤ 25 points vs > 25 points).
- *S aureus* in lesional skin at baseline ($<$ median vs \geq median) (at final analysis only).
- *S aureus* in non-lesional skin at baseline ($<$ median vs \geq median) (at final analysis only).
- Age (18 to 35 years of age vs 36 to 75 years of age).
- Age at onset of AD (< 18 years of age vs ≥ 18 years of age).
- Parent having a history of AD (presence vs absence).

- Sex (male vs female).
- Race (White vs non-White).
- Region (North America vs Europe/Australia).
- Blood eosinophil count at baseline (< 300 cells/ μL vs ≥ 300 cells/ μL).
- Aeroallergens (presence vs absence).
- Food allergies (presence vs absence).
- Contact allergies (presence vs absence).
- Asthma comorbidity (presence vs absence).

The MMRM will be fitted separately to each subgroup. The analysis for each subgroup will be performed if the subgroup has at least 20% of subjects in the ITT population.

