2.4 Sample Size

A sample size of 144 subjects in an overall 3:1:1:3 ratio of MEDI3506 CCI : MEDI3506 CCI : MEDI3506 CCI : pooled placebo will provide at least 90% power to detect a statistically significant difference in the percent change from baseline to Week 16 in EASI score between the highest dose of MEDI3506 and pooled placebo in a responder subgroup, assuming a 35% point difference between placebo and MEDI3506 at the highest dose, based on a SD of 40% points, a two-sided 10% alpha level and 50% of subjects in the responder subgroup. Based on identical assumptions, the sample size provides > 99% power to detect a statistically significant dose response in percent change from baseline to Week 16 in EASI score in all-comers.

The calculations for dose-response assume that percent change from baseline to Week 16 in EASI score will increase monotonically with the administration of higher MEDI3506 doses. The power was calculated using a multiple comparison procedure with modelling techniques (MCP-Mod) (Bretz et al, 2005) with 4 candidate models for the dose response (linear, maximum effect attributable to the drug [E_{max}], and 2 Hill- E_{max} models). Randomization will be stratified by total IgE (< 150 kU/L or \geq 150 kU/L) at screening. The sample size calculations were performed using the R statistical computing software.

To allow for the possibility that \leq 5% of the subjects per treatment group (for MEDI3506 CCI and placebo) may be ineligible for the ITT population, the total sample size will comprise approximately 152 subjects (58 MEDI3506 CCI, 18 for MEDI3506 CCI, 18 for MEDI3506 CCI, and 58 for pooled placebo) randomized approximately to 3:1:1:3 ratio overall to the treatment groups.

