3 STATISTICAL METHODS

3.1 General Considerations

In general, unless specified otherwise, baseline is defined as the last non-missing assessment prior to dosing. If the baseline is missing following the above definition, baseline evaluations will not be imputed and will be considered as missing. All safety analyses will be performed on the As-treated population. All PK analyses will be conducted using the PK-population. Immunogenicity evaluation will be based on the As-treated population. All other analyses will be performed on the ITT population unless stated otherwise. All data will be provided in data listings sorted by treatment group and subject number. The placebo CCI groups will be pooled for planned analyses, except where stated otherwise. All tabular summaries will be presented by treatment group. Categorical data will be summarized by the number and percentage of subjects in each category. Continuous variables will be summarized by descriptive statistics including number of subjects, mean, standard deviation (SD), median, minimum, and maximum. All statistical tests will be two-sided at an alpha = 0.1 significance level unless stated otherwise.

Day 1 is the first dosing date. Prior to Day 1, study days will be calculated as (sample collection date – Day 1). After Day 1, study days will be calculated as (sample collection date – Day 1 + 1).

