3.4.2.4 Subgroup Analyses

The consistency of the detected overall treatment effect on the IGA response at Week 16 will be assessed in a subgroup of subjects. A logistic regression model including treatment group, randomization stratum (total serum IgE level < 150 kU/L or ≥ 150 kU/L), and baseline IGA as categorical factors, will be used in a similar way as described in Section 3.4.2.3 for the following subgroup populations of interest:

- Total serum IgE level (< 150 kU/L vs ≥ 150 kU/L).
- IGA score (3 vs 4).
- Baseline EASI (≤ 25 points vs > 25 points).
- *S aureus* in lesional skin ($<$ median vs \geq median) (at final analysis only).
- *S aureus* in non-lesional skin ($<$ median vs \geq median) (at final analysis only).
- Age (18 to 35 years of age vs 36 to 75 years of age).
- Age at onset of AD (< 18 years of age vs ≥ 18 years of age).
- Parent having a history of AD (presence vs absence).
- Sex (male vs female).
- Race (White vs non-White).
- Region (North America vs Europe/Australia).
- Blood eosinophil count (< 300 cells/ μ L vs ≥ 300 cells/ μ L).
- Aeroallergens (presence vs absence).
- Food allergies (presence vs absence).
- Contact allergies (presence vs absence).
- Asthma comorbidity (presence vs absence).

The logistic regression will be fitted separately to each subgroup. The analysis for each subgroup will be performed if the subgroup has at least 20% of subjects in the ITT population.

Similarly, the consistency of the detected overall treatment effect on the percentage of subjects achieving EASI 75 at Week 16 will be assessed in subgroup of subjects described above using a similar logistic regression model as described previously (Section 3.4.2.3).

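### Subgroup consistency is to be assessed from separate model fits in each level, and the difference in treatment effect between levels is never estimated, given an interval or tested.

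*SAP*

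**What the plan says.** SAP 3.4.1.5 gives the aim for the primary endpoint: "The consistency of the overall treatment effect on the primary endpoint will be assessed in subgroups of subjects". It lists 16 two-level factors, two of which (S aureus in lesional and in non-lesional skin) are for the final analysis only. The method is "The MMRM will be fitted separately to each subgroup", for each level that holds at least 20% of the ITT population.

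SAP 3.4.2.4 uses the same list for IGA response at Week 16, where "The logistic regression will be fitted separately to each subgroup", and extends this to EASI 75.

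The model in SAP 3.4.1.3 reports adjusted differences from placebo with 90% CIs and p-values. SAP 3.1 sets the test level: "All statistical tests will be two-sided at an alpha = 0.1 significance level unless stated otherwise". Protocol 4.8.3.5 only defers subgroup analyses to the SAP. SAP section 5, on post hoc identification of responders, describes no interaction analysis. Neither document states how a factor would be judged consistent or inconsistent.

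**The concern.** Consistency concerns the difference in treatment effect between the two levels of a factor. Separate fits give an effect, an interval and a p-value inside each level, but not that difference or its precision.

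A reader of the tables is left to compare two within-level results, and the p-values are the easiest thing to compare. When a sample is split, significance in one level and not in the other can arise by chance with an identical true effect. How often depends on the power inside each level, not on any real heterogeneity. The sample size section is framed around a responder subgroup, so an apparent contrast of this kind could influence which patients are studied next.

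**Working it through.** **Inputs.** SAP 2.4: "A sample size of 144 subjects in an overall 3:1:1:3 ratio", which is 54:18:18:54; "assuming a 35% point difference between placebo and MEDI3506 at the highest dose, based on a SD of 40% points"; and "a two-sided 10% alpha level and 50% of subjects in the responder subgroup". SAP Appendix 1: maximum effect over placebo of 35 for EASI percent change; planning rates, read as percentages, of 10 v 30 for IGA and 15 v 35 for EASI 75. SAP 3.4.1.5: the 20% floor, so splits with both levels analysed run from 50:50 to 20:80.

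**The plan's own figures.** Power ≈ Φ(d/SE − 1.645), with SE = 40√(2/n) and n per arm.
- Responder half, 27 v 27: SE = 10.89; Φ(3.215 − 1.645) = 94%. The SAP says it "will provide at least 90% power to detect a statistically significant difference in the percent change from baseline to Week 16 in EASI score" in that subgroup, so this agrees.
- All-comers, 54 v 54, 35 points: 99.8%. The SAP's all-comers figure (above 99%) is for the dose-response test. The two-group value is in line with it, and simulated MCP-Mod power over several assumed dose sets (the doses are redacted) was 99.8% to 99.9%.

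**Chance that exactly one level is significant when the true effect is identical.** With level-specific powers p1 and p2, this is p1(1 − p2) + p2(1 − p1). The comparison is top dose v pooled placebo at two-sided 10%. For proportions, SE = √[(pA(1 − pA) + pB(1 − pB))/n].

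| Endpoint and constant effect | Split | p1, p2 | Exactly one significant |
|---|---|---|---|
| EASI % change, 35 points (planned) | 50:50 | 0.942, 0.942 | 11% |
| | 30:70 | 0.801, 0.985 | 21% |
| | 20:80 | 0.651, 0.992 | 35% |
| EASI % change, 17.5 points (assumption) | 50:50 | 0.485, 0.485 | 50% |
| | 20:80 | 0.265, 0.651 | 57% |
| IGA, 10% v 30% | 50:50 | 0.600, 0.600 | 48% |
| | 20:80 | 0.328, 0.775 | 59% |
| EASI 75, 15% v 35% | 50:50 | 0.540, 0.540 | 50% |
| | 20:80 | 0.294, 0.713 | 59% |

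Example, first row: 2 × 0.942 × 0.058 = 0.11. Example, IGA at 50:50: SE = √(0.30/27) = 0.1054; Φ(0.20/0.1054 − 1.645) = 0.600; 2 × 0.600 × 0.400 = 0.48.

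The 17.5-point row assumes 35 points in half the subjects and none in the rest: 0.5 × 35 = 17.5. All-comers two-group power is then 74%.

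**Comparator.** An interaction test at 10% flags a truly constant effect in 10% of factors whatever the overall effect, or 1.6 of 16. Its precision for EASI percent change at a 50:50 split: SE = 40√(4/27) = 15.4 points. Power is Φ(17.5/15.4 − 1.645) = 31% for a 17.5-point difference between levels and Φ(35/15.4 − 1.645) = 74% for 35 points.

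These are Week 16 two-sample approximations, with no dropout, no data lost to rescue and no gain from covariates.

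**The case against.** The strongest reply is that the SAP contains no rule that one significant and one non-significant level means inconsistency. Estimates and 90% CIs will be available in each level. Because the levels are disjoint, a reader could derive the between-level difference and its SE from the two fits. This stands as far as it goes: discordant significance is a risk of interpretation, not a planned decision. It does not supply the missing comparison, which the SAP does not plan to report.

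Three stronger readings are tempting, and the documents do not support them.
- **About half of all factors will look inconsistent.** A reader might get there by taking the 90% power in SAP 2.4 as the overall power. That figure belongs to a responder subgroup of 50% of subjects; the all-comers figure is above 99%. For EASI percent change at the planned 35 points and an even split, the rate is 11% (16 × 0.11 = 1.8 factors), close to the 1.6 from interaction tests. About half needs an all-comers effect near 15 to 20 points, or the IGA and EASI 75 endpoints. Sixteen is also a maximum: two factors are for the final analysis only, and a factor with a level under 20% cannot be discordant.
- **The plan produces false responder signals by design.** Responder identification sits in SAP section 5: post hoc, with its own analysis plan and outside the CSR.
- **The smallest fits cannot be estimated.** SAP 3.4.1.3 allows a simpler covariance structure if the unstructured one does not fit, and the calculation here does not use the 18-subject arms.

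It is also fair that an interaction test has low power. That limits the remedy but does not favour separate fits.

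**Conclusion.** The point holds. SAP 3.4.1.5 and 3.4.2.4 state an aim of assessing consistency, and the planned output does not measure it, because no between-level difference is estimated, given an interval or tested.

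The size of the risk is conditional on within-level p-values being read as evidence of inconsistency. For a constant top-dose effect, that reading would mislead for about 11% to 35% of factors on EASI percent change at the planned effect. It would mislead for about 50% to 57% if the all-comers effect is 17.5 points, and for about 48% to 59% on IGA and EASI 75 at the Appendix 1 rates. The ranges run from a 50:50 to a 20:80 split. The corresponding rate for an interaction test is 10% throughout.

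**What to change.** For each factor, fit one model on the full ITT population with treatment-by-subgroup terms; for the MMRM, include treatment × visit × subgroup as well. Report the top-dose v placebo difference at Week 16 in each level with its 90% CI, and the between-level difference (the interaction) with its 90% CI and p-value. Do the same in the IGA and EASI 75 logistic models. State in both SAP sections that within-level p-values are not used to judge consistency.

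The cost is SAP wording and modest programming. There are two downsides. A common covariance matrix across levels is assumed. The interaction test has low power, about 31% for a 17.5-point and 74% for a 35-point between-level difference at an even split. The text should therefore put the emphasis on the estimate and interval, and say that a non-significant interaction does not prove consistency.

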3.4.2 Secondary Efficacy Endpoints and Analyses

3.4.2.1 Secondary Efficacy Endpoints

Secondary efficacy endpoints will be measured up to Week 16 for on-therapy effects and at time points beyond the end of treatment for off-therapy effects.

IGA

The IGA consists of a 5-point severity scale from clear to severe disease (0 = clear, 1 = almost clear, 2 = mild disease, 3 = moderate disease, and 4 = severe disease). The secondary efficacy IGA endpoint is the percentage of subjects achieving both an IGA score of 0 (clear) or 1 (almost clear) and a reduction from baseline of ≥ 2 points at Week 16.

EASI including Percentage BSA Affected by AD

Secondary efficacy endpoints based on EASI include, as follows:

- Percentage of subjects achieving a 90% reduction from baseline in EASI score (EASI 90) at Week 16
- Percentage of subjects achieving a 75% reduction from baseline in EASI score (EASI 75) at Week 16
- Percentage of subjects achieving a 50% reduction from baseline in EASI score (EASI 50) at Week 16
- Change from baseline to Week 16 in the percentage of BSA affected by AD, as assessed by EASI.

Pruritus NRS

Pruritus will be assessed using an NRS (0 to 10) with 0 = no itch and 10 = worst imaginable itch. Daily peak pruritus NRS assessments will be summarized as weekly means. The weekly mean score will be set to missing if > 3 assessments are missed in that 7-day period. Baseline will be defined as an average of the last 7 days prior to study drug being administered. If more than 3 days have missing data in the baseline period, the baseline period will be shifted back to the last 7-day period which includes at least 4 non-missing days.

The secondary efficacy endpoints based on pruritus NRS include:

- Change from baseline to Week 16 in weekly mean of daily peak pruritus NRS, and
- Percentage of subjects achieving a reduction of ≥ 3 from baseline to Week 16 in weekly mean of daily peak pruritus NRS.

Skin Pain NRS

Skin pain (ie, worst skin pain experienced in the previous 24 hours) will be assessed using an NRS (0 to 10) with 0 = no pain and 10 = worst imaginable pain. Daily peak skin pain NRS assessments will be summarized as weekly means. The weekly mean score will be set to missing if > 3 assessments are missed in that 7-day period. Baseline will be defined as an average of the last 7 days prior to investigational product being administered. If more than 3 days have missing data in the baseline period, the baseline period will be shifted back to the last 7-day period which includes at least 4 non-missing days.

The secondary efficacy endpoint based on skin pain NRS is change from baseline to Week 16 in weekly mean of daily peak skin pain NRS.

SCORAD

The secondary efficacy endpoint based on SCORAD is the percent change from baseline to Week 16 in SCORAD, which is calculated as presented in [Table 5 \(European Task Force on Atopic Dermatitis, 1993\)](#).

Table 5 SCORAD Calculation

Component	Definition	Grading	Score
Extent (A)	
 head and neck upper limbs (anterior/posterior) lower limbs (anterior/posterior) anterior trunk back genitals hand (right/left) 	
 head and neck: 9% upper limbs: 9% each lower limbs: 18% each anterior trunk: 18% back: 18% genitals: 1% hand: 1% each 	Sum of each extent item score to give a total extent score A (range 0-102)
Intensity (B)	
 erythema edema/papulation oozing/crusts excoriations lichenification dryness 	Each intensity item is defined on a 4-point ordinal scale: 0 = absent 1 = mild 2 = moderate 3 = severe	Sum of each intensity item score to give a total intensity score B (range 0-18)
Subjective Symptoms (C)	
 pruritus sleep loss 	Each symptom has an NRS (0-10) where 0 is no pruritus/sleep loss and 10 is the worst imaginable pruritus/sleep loss.	Sum of each subjective symptom score to give a total symptom score C (range 0-20)
Objective SCORAD Score	NA	NA	$(A/5) + (7 \times B/2)$
SCORAD Score	NA	NA	$(A/5) + (7 \times B/2) + C$

NA = not applicable.

Patient Global Impression of Severity (PGI-S)

The PGI-S is a tool that allows patients to rate the severity of a condition. The PGI-S comprises a single question of, “Would you describe your AD or eczema as no symptoms, very mild, mild, moderate, severe or very severe?” The secondary efficacy endpoint based on this is PGI-S score at Week 16.

5-D Pruritus Score

A secondary efficacy endpoint includes change from baseline to Week 16 in 5-D pruritus score. 5-D pruritus score is calculated as presented in [Table \(Elman et al, 2010\)](#).

Table 6 **5-D Pruritus Score Calculation**

Domain	Definition	5-D Pruritus Score
Duration	Single-item domain score (range 1-5)	Range 1-5
Degree	Single-item domain score (range 1-5)	Range 1-5
Direction	Single-item domain score (range 1-5)	Range 1-5
Disability	Four items that assess the impact of itching on daily activities 
 • sleep (range 1-5) • leisure/social (range 1-5) • housework/errands (range 1-5) • work/school (range 1-5) 	Highest score on any of the four items
Distribution	Sixteen affected body parts (sum 0-16)	
 • 1 = sum of 0-2 • 2 = sum of 3-5 • 3 = sum of 6-10 • 4 = sum of 11-13 • 5 = sum of 14-16
5-D Pruritus	NA	Sum of five domains

NA = not applicable.

Patient-Oriented Eczema Measure (POEM)

The Patient-Oriented Eczema Measure (POEM) is a 7-item questionnaire for assessing disease symptoms including dryness, itching, flaking, cracking, sleep loss, bleeding, and weeping occurring in the past week. Each item is scored on a 5-point scale with 0 = no days, 1 = 1 to 2 days, 2 = 3 to 4 days, 3 = 5 to 6 days, and 4 = every day. The total POEM score is calculated by summing the score of each item resulting in a maximum of 28 and a minimum of 0, with higher values indicating severe disease ([Charman et al, 2004](#)). The secondary efficacy endpoint based on this questionnaire is the change from baseline to Week 16.

Dermatology Life Quality Index

The Dermatology Life Quality Index (DLQI) is a 10-item, patient-completed, health-related quality of life assessment of dermatology conditions with a recall period of 1 week. The DLQI captures perceptions of dermatology-related symptoms and feelings; impacts on daily activities, leisure, work or school, personal relationships; and the side effects of treatment. Each item is scored on a 4-point Likert scale with 0 = not at all/not relevant, 1 = a little, 2 = a lot, and 3 = very much ([Basra et al, 2008](#)). The DLQI score is calculated by summing the score of each item resulting in a maximum of 30 and a minimum of 0. The higher the score, the more quality of life is impaired. The secondary efficacy endpoint based on DLQI is change from baseline in DLQI score to Week 16.

3.4.2.2 Handling of Dropouts and Missing Data

If any component of SCORAD, 5-D Pruritus Score, POEM, DLQI or EASI score is missing, the calculation of the score will be set to missing.

For the analysis of efficacy responder endpoints, including the proportion of subjects achieving both IGA score of 0 (clear) or 1 (almost clear) and a reduction from baseline of ≥ 2 points, EASI 50, EASI 75, EASI 90 and peak pruritus NRS responders, subjects who discontinue investigational product, withdraw from the study, or require rescue therapy will be considered as non-responders. For the EASI 75 and IGA endpoints, additional sensitivity analyses will be performed using the last non-missing post-baseline value carried forward approach to assess the impact of including efficacy data beyond the use of rescue therapies. For subjects who receive rescue therapies, the last response value recorded on the day of, or prior to, the subject received a prohibited rescue therapy will be carried forward.

The continuous efficacy endpoints, including, percent change from baseline to Week 16 in SCORAD, change from baseline to Week 16 in peak pruritus NRS, skin pain NRS, 5-D pruritus (itch) score, percentage of BSA affected by AD, POEM, and DLQI will be analyzed using MMRM. All data points for subjects in the ITT population will be included in the analysis, up to and including the day the rescue therapy is used.

